#### 12.2. Treatment allocation

All trial participants will receive atezolizumab.

Participants will be randomised between continuing atezolizumab only and continuing atezolizumab with a course of radiotherapy on a 1:1 basis.

Treatment allocation is by minimisation with a random element; balancing factors will be randomising centre, line of treatment (first v  $2_{nd}/3_{rd}$ ), metastasis of liver and/or bone (yes/no) and disease status (stable vs progressive disease).

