## 5.2. Source of participants

Participants will be recruited from approximately 20 participating sites in the UK. Potential participants will be identified in oncology clinics.

ICR-CTSU encourages investigators to consider equality, diversity and inclusion when recruiting participants into its trials.

Eligibility criteria are listed below – if there are any queries regarding a potential participant's eligibility for RE-ARM please contact the RE-ARM trial manager ([contact]).

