# 12.4. Statistical analysis plan

#### **Primary endpoint**

Objective response rate (CR [complete response] + PR [partial response]) at 9 weeks after start of study treatment will be compared between the two trial arms using a chi-squared test or Fisher's exact test, as appropriate, and an estimate of the difference in proportions of responders calculated with a 95% confidence interval.

Blinded central review of objective responses will be conducted retrospectively.

A supplementary analysis will consider objective response rate at 9 weeks as above, but incorporating the (planned) radiotherapy site within the RECIST v1.1 assessment (where it met the criteria for a RECIST v1.1 target lesion) to assess the impact of excluding this lesion in the principal analysis.

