#### Secondary endpoints

Objective response rate according to iRECIST and clinical benefit according to RECIST v1.1 will be compared between trial arms as per the primary endpoint. Best response will be tabulated according to trial arm.

Duration of response, time to progression, progression free survival and overall survival will be presented according to trial arm using Kaplan-Meier survival plots and analysed using log-rank tests and Cox proportional hazards models. Rates of progression free and overall survival will be estimated at 12 and 24 months.

Treatment-related toxicity will be presented according to grade and trial arm.

Quality of life data will be analysed using standard algorithms to derive scores and handle missing data according to the questionnaire's scoring manual. The primary outcome measure for patient reported quality of life will be overall quality of life measured by the EORTC QLQ-C30 global health/quality of life subscale score, which will be treated as a continuous variable. Subscale scores will be compared between treatment groups at individual time points, as well as the change from baseline to Week 9 and 6 months, using ANCOVA adjusting for baseline scores. Additional analyses of EORTC QLQ-C30 subscales will dichotomise change in subscale scores from baseline to each follow-up timepoint according to whether or not patients have experienced a deterioration of >10 points, and compared between groups using chi-squared tests or Fisher's exact test, as appropriate. Analyses to account for the longitudinal nature of the data (generalised estimating equations) may also be used. Secondary QoL outcomes of interest include the EORTC QLQ-C30 subcales for physical functioning, role functioning and fatigue, individual domains and utility scores from the EQ-5D-5L.

QoL sub-study patients who are still being treated with atezolizumab at 12 months will be asked to complete the questionnaire at this timepoint. QoL data for this subset of patients will be compared with their baseline QoL data taking into account relevant covariates including other treatments taken, to explore the impact of long term use of atezolizumab on QoL.

Exploratory analyses will be conducted to investigate whether response varies according to site of target lesion. Details will be specified in the Statistical Analysis Plan.

Analyses of efficacy outcomes will be by intention-to-treat; safety analyses will be in the per protocol population.

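### Allocation is minimised on three clinical factors, but the protocol fixes an unadjusted test and risk difference for 9-week response: a small, conditional loss of precision

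*Protocol*

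**What the plan says.** Protocol section 12.2 (Treatment allocation): "Treatment allocation is by minimisation with a random element; balancing factors will be randomising centre, line of treatment", then "metastasis of liver and/or bone (yes/no) and disease status (stable vs progressive disease". Section 5.2 expects "approximately 20 participating sites in the UK". Section 7 lists line of treatment, liver/bone metastasis and disease status among the items collected at randomisation.

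Section 12.4, under Primary endpoint, says that 9-week objective response "will be compared between the two trial arms using a chi-squared test", or Fisher's exact test where appropriate, with an "estimate of the difference in proportions of responders calculated with a 95% confidence interval". No covariate or stratum is named. Under Secondary endpoints, iRECIST response and clinical benefit are compared in the same way. The time-to-event endpoints are shown with "Kaplan-Meier survival plots and analysed using log-rank tests and Cox proportional hazards models"; nothing is said either way about strata or covariates. The one between-arm comparison in 12.4 with an explicit adjustment is the quality-of-life ANCOVA on baseline score. The section closes by leaving further details of analysis methods to the SAP.

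Section 12.1 sizes the trial with an unadjusted one-sided z-test at 0.2. It sets an interim futility boundary of 0, also expressed as a comparison of response counts, and a final boundary of 0.68.

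**The concern.** Minimisation removes most of the chance imbalance between arms in the factors it balances. The usual variance of a difference in proportions is computed as though that imbalance could still occur. When the factors predict response, the reported standard error exceeds the true sampling variability, the confidence interval is too wide, and the test rejects too rarely.

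For the response endpoints the protocol itself names the test and the estimate, so this is a stated method and not a detail awaiting the SAP. The trial is small: at the design rates it expects 46 × 0.15 + 46 × 0.30 = 20.7, about 21 responders. At stake is a modest amount of precision that could be recovered from data already collected.

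**Working it through.** **Inputs from the protocol (12.1, 12.2, 5.2).** Response 15% v 30%, 1:1 allocation, one-sided 0.2, power 80%, 92 evaluable (46 per arm), interim at 23 per arm with boundary 0, final boundary 0.68, four balancing factors including about 20 centres.

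**The plan's own figure.** For a fixed design, n per arm = [z(0.8)√(2 × 0.225 × 0.775) + z(0.8)√(0.15 × 0.85 + 0.30 × 0.70)]² / 0.15² = [0.8416 × (0.5906 + 0.5810)]² / 0.0225 = 43.2, so 44 per arm or 88 in total. With the futility look, 46 per arm gives 80.4 to 81.2% power by normal approximation (depending on the variance used) and 79.5% by exact binomial calculation. The stated 92 is reproduced. Allowing for 10% non-evaluable, 92/0.9 = 102.2, in line with 102.

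**Assumptions.** The documents give no prognostic strength, so the same odds ratio is assumed for each of three binary factors (prevalence 40/50/50%), with no centre effect. Allocation is minimised on the three factors and 20 centres with an 80% biased coin. There are 92 patients, a final analysis only at one-sided 0.2, and 15,000 simulated trials per row, so the Monte Carlo error on a rejection rate is about 0.3 point. Adjusted means a risk difference from a linear model in the three factors; CMH is the stratified test.

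| Odds ratio per factor | True effect | Unadjusted SE | True SD | SE/SD | Rejects: unadjusted | Adjusted | CMH |
|---|---|---|---|---|---|---|---|
| 1.5 | 0 | 0.0733 | 0.0739 | 0.99 | 20.7% | 20.2% | 20.4% |
| 1.5 | +15 points | 0.0845 | 0.0847 | 1.00 | 82.5% | 82.0% | 81.1% |
| 2 | 0 | 0.0733 | 0.0730 | 1.00 | 20.9% | 20.6% | 20.8% |
| 2 | +15 points | 0.0846 | 0.0829 | 1.02 | 82.8% | 82.9% | 81.9% |
| 3 | 0 | 0.0732 | 0.0714 | 1.03 | 20.0% | 20.2% | 20.3% |
| 3 | +15 points | 0.0846 | 0.0809 | 1.05 | 83.4% | 84.6% | 83.6% |
| 5 | 0 | 0.0732 | 0.0693 | 1.06 | 19.0% | 20.0% | 20.3% |

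Power at an odds ratio of 5 is not available.

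**Check by hand at odds ratio 3.** Power ≈ Φ((0.15 − c × SE)/SD) with c = 0.8416.
- Unadjusted: (0.15 − 0.0712)/0.0809 = 0.974, giving 83.5%.
- Adjusted (SE 0.0807, SD 0.0806): (0.15 − 0.0679)/0.0806 = 1.018, giving 84.6%.
- With the plan's final boundary c = 0.68, ignoring the interim look: (0.15 − 0.0575)/0.0809 = 1.143 (87.3%) against (0.15 − 0.0549)/0.0806 = 1.180 (88.1%), a gain of about 0.8 point.

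**What the gain is.** At odds ratio 3 the true SD hardly changes on adjustment (0.0809 v 0.0806), because minimisation has already delivered the balance. Adjustment mainly corrects the reported standard error. The CMH test gains almost nothing at odds ratio 3 and gives up 1.4 points at 1.5 (82.5% to 81.1%), so the choice of adjusted method matters.

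**The case against.** The strongest reply is that the unadjusted analysis is coherent and valid. It matches the z-test used for sizing, its type I error stays within about one point of 0.20 across the assumed range, and at odds ratios of 1.5 to 2 adjustment gains nothing. All of this stands. It makes the point an improvement, not the correction of an error.

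A second reply is that adjustment can do harm at the interim, and this stands too. In a simulation of 46 interim patients, the sign of an adjusted difference disagreed with the count rule in about 4 to 10% of trials. In 7 to 45% of the datasets, depending on the assumed effects, an arm or factor level had no responders, so a logistic model would have no finite estimate. The adjustment should therefore be confined to the final analysis.

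Three stronger readings are tempting but unsupported.
- A reader might infer that the log-rank and Cox analyses ignore the factors. The protocol is silent on this and leaves further detail to the SAP. The standard-error argument would not carry over either: in an approximate simulation (500 trials, factor hazard ratio 1.5, no treatment effect) the adjusted Cox standard error was slightly larger (0.214 v 0.211). Duration of response exists only for about 21 responders, too few for eight strata.
- A reader might take the loss as certain. It depends on prognostic strengths that the protocol does not give.
- A reader might turn a 5% smaller standard error into 92 × 0.95² = 83 patients. That treats a corrected standard error as new information; the simulated power gain is about one point.

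**Conclusion.** The point holds in a limited form. For 9-week response, iRECIST response and clinical benefit, the protocol minimises on three clinical factors and then fixes an analysis that does not use them. If the factors predict response, the unadjusted standard error is too large: by about 0 to 2% at odds ratios of 1.5 to 2 per factor, and about 3 to 6% at 3 to 5. The power cost is nil at 1.5 to 2 and about one point at 3. With weak factors, covariate adjustment costs about half a point (82.5% v 82.0% at 1.5). The test is mildly conservative when the factors are strong and is not invalid.

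These sizes rest on the assumed odds ratios, prevalences and biased-coin probability, and on linear-model adjustment; logistic marginal standardisation was not simulated.

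**What to change.** In section 12.4, and in the SAP to match:

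1. Make the final primary estimate a risk difference adjusted for line of treatment (first v second/third), liver/bone metastasis and disease status. Marginal standardisation from a main-effects logistic model is suitable. A Mantel-Haenszel risk difference is an alternative, but the CMH results above argue against splitting into all eight cells without checking the power first.
2. Pre-specify a fallback for sparse data, for example a linear model with robust standard errors if an arm or factor level has no responders or the logistic model fails to converge.
3. Compare the adjusted z statistic with the final boundary of 0.68, and report the unadjusted test and difference as supportive.
4. Use the same method for iRECIST response and clinical benefit.
5. Keep the interim futility rule as the unadjusted count comparison in 12.1.
6. State that centre is left out of the model because about 20 sites share 102 patients.

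The cost is protocol and SAP wording, settled before any unblinded comparison. No new data are needed.

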## 12.3. Endpoint definitions

#### 12.3.1. Primary endpoint

Objective response (CR [complete response] + PR [partial response] according to RECIST v1.1) at 9 weeks after start of study treatment.

#### 12.3.2. Secondary endpoints

- Objective response according to iRECIST (iCR + iPR)
- Clinical benefit at 9 weeks according to RECIST v1.1 (CR, PR, SD)
- Best response up to 6 months, defined as specified in A1.10
- Duration of response, defined as time from objective response until recurrence or progressive disease (PD)
- Time to progression, defined as time from randomisation until confirmation of progression
- Progression free survival, defined as time from randomisation until progression or death from any cause
- Overall survival, defined as time from randomisation until death from any cause
- Treatment related toxicity (CTCAE v5)

• Patient reported quality of life (assessed using the EORTC QLQ-C30 and EQ-5D-5L questionnaires) at 9 weeks and 6 months for all patients participating in the QoL substudy. In addition any QoL sub-study patients still being treated with atezolizumab at 12 months should be asked to complete the EORTC QLQ-C30 and EQ-5D-5L at this timepoint. The primary outcome measure will be overall quality of life, measured by the EORTC QLC-C30 qlobal health/QoL subscale score.

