# 8.4. Primary endpoint assessment (9 weeks after start of study atezolizumab):

In addition to the above assessments:

- CT chest abdomen pelvis (CAP)
- RECIST v1.1 assessment

Primary endpoint assessment should be conducted nine weeks after the start of study treatment, irrespective of any treatment gaps that may have occurred.

Subsequent CT CAP assessments should be conducted every 9 weeks in the first year, then every 12 weeks in the second year until treatment discontinuation. RECIST v1.1 assessments should be conducted on each scan until RECIST v1.1 progression. CT CAP can be conducted according to local practice in line with RECIST imaging recommendations (34). This consists of, as a minimum, use of contiguous slices, with a slice thickness of ≤5mm and IV contrast (unless contraindicated). RECIST assessments should be conducted in accordance with the details in Appendices A1. RECIST and A2. iRECIST.

The planned site of radiotherapy, as specified at randomisation, should not be used for RECIST v1.1 assessment, irrespective of whether or not the participant was allocated to receive radiotherapy. However, please record the measurement for this lesion on the dedicated eCRF.

If atezolizumab is being withheld, CT CAP should still take place at the expected time-points unless the patient has permanently discontinued treatment.

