# 8.10.1. Sub-study schedule of assessments

Time point (all week/month numbers relate to the start of on-trial atezolizumab)  Activity	Screening	Baseline – post randomisation	Fraction 4 or 5 of RT (RT group only)	Week 3	Week 9 (Primary endpoint)	RECIST v1.1 progression	6 months	12 months
Translational sub-study sample acquisition schedule								
Blood: EDTA 10ml x 3, Tempus 3ml		Х	Х	Χ	Х	X 		
Blood: Streck 10ml		Х			Х	X 		
Access to FFPE blocks from diagnostic procedures 								
Quality of Life (QoL) sub-study schedule								
EORTC QLQ-C30 and EQ-5D-5L	X 				Х		Χ	X 

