#### 9.2.8. Dose modifications – atezolizumab

Atezolizumab dose reductions are not recommended. Recommended treatment modifications in the case of adverse reactions are detailed below.

Immune related adverse reaction	Severity (NCICTCAE v5)	Treatment modification
Pneumonitis	Grade 1	Consider treatment delay, monitor every 2-3 days
	Grade 2	Withhold atezolizumab
		Treatment may be resumed when the event improves to Grade 0 or Grade 1 within 12 weeks, and corticosteroids have been reduced to ≤ 10 mg prednisolone or equivalent per day
	Grade 3 or 4	Permanently discontinue atezolizumab
Hepatitis	Grade 2:	Withhold atezolizumab

Immune related adverse reaction	Severity (NCICTCAE v5)	Treatment modification
	(ALT or AST > 3 to 5 x upper limit of normal [ULN] or blood bilirubin > 1.5 to 3 x ULN)	Treatment may be resumed when the event improves to Grade 0 or Grade 1 within 12 weeks and corticosteroids have been reduced to ≤ 10 mg prednisolone or equivalent per day
	Grade 3 or 4:	Permanently discontinue atezolizumab
	(ALT or AST > 5 x ULN	Consider hepatology referral
	or	
	blood bilirubin > 3 x ULN)	
Colitis	Grade 2 or 3 diarrhoea	Withhold atezolizumab
	<pre>(increase of ≥ 4 stools/day over baseline) or Symptomatic colitis</pre>	Treatment may be resumed when the event improves to Grade 0 or Grade 1 within 12 weeks and corticosteroids have been reduced to ≤ 10 mg prednisolone or equivalent per day  Consider gastroenterology referral
	Grade 4 diarrhoea or colitis (life threatening; urgent intervention indicated)	Permanently discontinue atezolizumab
Hypothyroidism or	Symptomatic	Withhold atezolizumab
hyperthyroidism		Hypothyroidism:
		Treatment may be resumed when symptoms are controlled by thyroid replacement therapy and TSH levels are decreasing
		Hyperthyroidism:
		Treatment may be resumed when symptoms are controlled by anti-thyroid medicinal product and thyroid function is improving
		Consider endocrinology referral
Adrenal insufficiency	Symptomatic	Withhold atezolizumab
		Treatment may be resumed when the symptoms improve to Grade 0 or Grade 1 within 12 weeks and corticosteroids have been reduced to ≤ 10 mg prednisolone or equivalent per day and patient is stable on replacement therapy
		Consider endocrinology referral

Immune related adverse reaction	Severity (NCICTCAE v5)	Treatment modification		
Hypophysitis	Grade 2 or 3	Withhold atezolizumab		

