# 9.2.9. Missed doses

If a planned dose of atezolizumab is missed it should be administered as soon as possible; it is recommended not to wait until the next planned dose. The schedule of administration should be adjusted to maintain a 3-week interval between doses. If a patient does not receive atezolizumab for more than 12 weeks trial treatment should be discontinued.

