### A5.5 Timing of data collection

Participants will be asked to complete the questionnaire after informed consent is obtained during their clinic visit at the following time points: i) screening, before treatment allocation is known, ii) 9 weeks (cycle 4), iii) 6 months, and iv) 12 months for patients still being treated with atezolizumab.

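### Appendix A5.5 equates the 9-week quality-of-life questionnaire with cycle 4, while the endpoint and schedules run by calendar; the two part once a dose is delayed or treatment stops.

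*Protocol*

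**What the plan says.** Section 12.3.2 defines patient-reported quality of life "at 9 weeks and 6 months for all patients participating in the QoL substudy". Section 8.3 lists the questionnaire at week 9 and six months, and at 12 months for those still on atezolizumab. The table in 8.10.1 ticks it under week 9 and says that "all week/month numbers relate to the start of on-trial atezolizumab". A footnote to that table requires the 6-month questionnaire for every sub-study patient; only the 12-month one is limited to patients still on the drug.

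Appendix A5.5 gives the collection instruction: "Participants will be asked to complete the questionnaire after informed consent is obtained during their clinic visit at the following time points". The list that follows contains "ii) 9 weeks (cycle 4), iii) 6 months, and iv) 12 months for patients still being treated with atezolizumab".

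Dosing can move. After a missed dose, section 9.2.9 says: "The schedule of administration should be adjusted to maintain a 3-week interval between doses". It ends trial treatment once more than 12 weeks pass without drug. For many immune-related events section 9.2.8 says: "Treatment may be resumed when the event improves to Grade 0 or Grade 1 within 12 weeks".

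For the primary endpoint assessment, section 8.4 fixes nine weeks from the start of treatment, "irrespective of any treatment gaps that may have occurred". Footnote 4 to the table in 8.10 makes a similar statement for CT.

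**The concern.** The endpoint is a calendar measurement in all sub-study patients. The appendix that sites will consult for collection attaches it to a treatment cycle and to a clinic visit. For a patient on schedule this makes no difference. For a patient whose dosing is on hold at week 9, the cycle 4 visit comes later, often once the event has settled. For a patient who has stopped, there is no such visit.

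These are patients in whom a loss of quality of life would be expected to show. Appendix A5.2 sets out to show that adding radiotherapy does not make quality of life worse. Section 12.4 compares the arms on change from baseline to week 9 by ANCOVA, and on deterioration of more than 10 points. Scores taken late or never taken would weaken both analyses. The analysis plan could describe or model such gaps, but it could not recover a week-9 answer that was never collected.

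**Working it through.** The protocol gives no sample size or expected difference for quality of life, so there is no stated figure to reproduce. The check is of timing and of what each section instructs.

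**Timing.** Inputs: 21-day cycles (9.2.1) and a gap of at most 12 weeks before treatment ends (9.2.9). I count that gap from the last dose given.

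- With no delay, cycle k starts at week 3 × (k − 1), so cycle 4 starts at week 3 × 3 = 9. The two labels agree.
- If one of the three intervals before cycle 4 lasts g weeks and the other two last 3, cycle 4 starts at week 3 + 3 + g = 6 + g.
- With g = 12, cycle 4 starts at week 6 + 12 = 18. A questionnaire tied to cycle 4 is then 18 − 9 = 9 weeks late.
- If treatment stops before the fourth dose, there is no cycle 4.

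Week 18 is the latest date after a single gap. Shorter holds give proportionately smaller delays.

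**Sections side by side.**

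| Place | What it fixes |
|---|---|
| 12.3.2 | 9 weeks and 6 months, all sub-study patients |
| 8.3 | Week 9, but under the heading for on-treatment assessments |
| 8.10.1 | Week 9, counted from first on-trial dose |
| 8.10 | Separate columns: week 9 holds only the CT; cycle 4 holds examination, bloods, medication and adverse event review, and dosing |
| 8.4 and footnote 4 of 8.10 | Independence from treatment gaps, expressly for the primary endpoint assessment and CT |
| 8.7 and 8.8 | Procedures after stopping; no questionnaire listed |
| A5.5 | Clinic visit, 9 weeks equated with cycle 4 |

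The main schedule therefore treats week 9 and cycle 4 as distinct, and A5.5 merges them. Because the routine clinical assessments sit in the cycle 4 column, a site looking for the clinic visit named in A5.5 could reasonably choose that one.

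**Effect on the comparison.** In each arm, let m be the share of patients held or stopped at week 9, and D the number of points by which their true week-9 change falls below that of the others. If these patients are lost, or are measured only after full recovery, the difference hidden between the arms is m × D in the radiotherapy arm minus m × D in the control arm. With equal m and equal D it is zero. The protocol gives neither quantity for either arm, so no size can be derived.

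**The case against.** The strongest reply is that A5.5 names 9 weeks first and adds cycle 4 only in brackets, as a gloss for the patient on schedule. Sections 8.3, 8.10.1 and 12.3.2 all give calendar week 9, and a site working from the schedule tables will use it. Section 8.4 opens by adding its scan to the assessments already listed, which include the week-9 questionnaire, so its rule on treatment gaps can arguably be read as covering the questionnaire too. Patients with dosing withheld still come for the week-9 CT. Section 8.8 keeps patients who stopped on the scan timetable until progression or new systemic treatment. Appendix A5.6 has the oversight committees monitor completion.

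Much of this stands. It rules out the stronger reading that a reader might take from A5.5: that the protocol moves collection to cycle 4 and drops patients who stopped. No section says that. Section 12.3.2 covers all sub-study patients, the footnote to 8.10.1 does so expressly at 6 months, and the cycle 4 wording does not touch the 6-month time point.

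A reader might also infer that the result is tilted towards showing no detriment. The documents do not establish this either. Both arms receive atezolizumab, and the holds in 9.2.8 are for its immune-related reactions. Section 11.5 lists diarrhoea and colitis among expected radiotherapy events, which makes extra holds in that arm plausible, but no rate is given.

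The reply does not remove the conflict. The items that 8.4 lists are only the CT and the RECIST assessment, so extending its rule to the questionnaire is an inference. The last sentence of 8.4 exempts patients who have permanently discontinued from the scan timetable that applies during a hold, so week-9 attendance after stopping is not certain. Monitoring completion shows missing forms; it does not tell a site which date is right.

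**Conclusion.** The inconsistency is real and is confined to collection. A5.5 ties the 9-week questionnaire to cycle 4 and a clinic visit, while the endpoint definition and the schedules use calendar time for all sub-study patients. A site that follows the cycle 4 wording could collect the score up to 9 weeks late after one maximum gap, or not at all in a patient who stopped earlier. That is a risk created by conflicting instructions, not an exclusion written into the protocol. It biases the week-9 comparison only if holds, stops or their effects on quality of life differ between arms; no numerical estimate is justified.

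Severity is minor to moderate. Participation in the sub-study is voluntary, A5.2 calls all its tests exploratory and unpowered, and the primary endpoint and sample size are unaffected. The correction is still worth making now, because a missed week-9 score cannot be recovered later.

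**What to change.** In A5.5, delete the bracketed cycle 4. State that the week-9 and 6-month questionnaires are due by calendar from the start of study atezolizumab, whether or not doses have been delayed or treatment has stopped. In 8.7 and 8.8, list both questionnaires for sub-study patients who are off treatment when they fall due. The 12-month questionnaire can stay limited to patients still on atezolizumab.

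The cost is about one sentence in A5.5, short entries in 8.7 and 8.8, and a few questionnaires collected outside dosing visits. No sample size, treatment rule or analysis method changes.
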